8.2.1.2. Myeloma Protein Measurements in Serum and Urine

Blood and 24-hour urine samples for M-protein measurements will be sent to and analyzed by a central laboratory. Only 1 serum and one 24-hour urine sample at each timepoint are required by the central laboratory to perform the following tests:

- Serum quantitative IgS
 - All participants will be evaluated for IgG, IgA, IgM, IgE, and IgD as indicated in [Table 3](#) and [Table 4](#).
- SPEP

- Serum IFE at screening and thereafter when M-protein is nonquantifiable
- Serum FLC assay
- 24-hour UPEP
- Urine IFE at screening and thereafter when a M-protein is nonquantifiable

Blood and 24-hour urine samples will be collected as specified in the SoA (see [Table 3](#) and [Table 4](#); see [Table 7](#) for the SoA for all participants as of Protocol Amendment 3) until the development of confirmed disease progression. If the 24-hour urine collection (UPEP) began before informed consent was obtained as part of routine patient care, the sample can be used in this study as long as it was sent to the central laboratory for analysis after the informed consent was obtained. Disease progression based on one of the laboratory tests alone must be confirmed by at least 1 repeat investigation performed 1 to 3 weeks later. Disease evaluations will continue beyond relapse from CR until disease progression is confirmed. Serum and urine IFE and serum FLC assay will be performed at screening and thereafter when a CR is suspected or maintained (when serum or 24-hour urine M-protein electrophoresis [by SPEP or UPEP] are 0 or nonquantifiable). For participants with light chain MM, both serum and urine IFE test will be performed routinely.

Serum IFE assay samples will be split into 2 aliquots, with 1 reserved for potential follow-on testing if daratumumab interference with IFE is suspected. As daratumumab is a monoclonal IgG antibody, additional serum samples may be used to monitor for potential daratumumab interference with the IFE.

Previous studies have demonstrated potential interference of therapeutic monoclonal antibodies with detection of endogenous myeloma M-protein on serum IFE ([McCudden et al 2015](#)). For participants with suspected daratumumab interference on SPEP, serum IFE, or both, a follow-up test will be run using anti-idiotype antibodies against daratumumab to remove antibody interference.

Participants who meet all other IMWG criteria for CR or sCR, and whose positive IFE is confirmed to be daratumumab, will be considered as having a CR or sCR.

8.2.1.5. Bone Marrow Examination

Bone marrow assessments to be performed locally and centrally are summarized in [Table 20](#).

Table 20: Bone Marrow Testing

	Local Testing	Central Testing
Screening	Disease characterization (morphology and either immunohistochemistry or immunofluorescence or flow cytometry). Cytogenetics by conventional karyotype or FISH.	MRD assessment: a portion of the bone marrow aspirate collected at screening will be sent to the central laboratory (see Section 8.2.1.6). A fresh bone marrow aspirate is preferred, but if a fresh bone marrow aspirate is not performed at screening because a sample is available within 42 days before administration of study treatment, obtain non-decalcified slides (bone marrow aspirate, touch preparation, or clot selection) or FFPE block (clot section only, no bone marrow biopsy).
CR, sCR	For response confirmation, additional bone marrow aspirates or biopsies (or both) will be performed locally to confirm sCR or CR. Response characterization (morphology by immunohistochemistry or immunofluorescence or flow cytometry). For sCR: Detection of kappa/lambda ratio by 2-4 color flow cytometry is strongly preferred. If flow cytometry is not available at site, either immunohistochemistry or immunofluorescence can be done; however, kappa/lambda ratio from analysis of ≥ 100 plasma cells is required to confirm sCR. If sCR is not met, repeat local testing for sCR with subsequent bone marrow examinations will be performed.	MRD assessment: a portion of the bone marrow aspirate collected for confirmation of CR/sCR will be sent to the central laboratory for MRD assessment. For participants who achieve CR and remain on study, an additional bone marrow aspirate will be obtained as indicated in Table 3 .

CR = complete response; FFPE = formalin-fixed, paraffin-embedded; FISH = fluorescence in situ hybridization;

MRD = minimal residual disease; sCR = stringent complete response.

8.2.1.6. Minimal Residual Disease Assessment

Bone marrow aspirate will be collected for MRD analysis, when bone marrow samples are obtained at screening, confirmation of CR/sCR, and subsequent timepoints after the first dose (see [Table 20](#)). Baseline bone marrow aspirate samples will be subjected to DNA sequencing to establish a MM clone for MRD monitoring. A fresh bone marrow aspirate at screening is required, if possible. By exception, non-decalcified diagnostic tissue slides (bone marrow aspirate, touch preparation or clot selection) or FFPE block (clot selection only, no bone marrow biopsy) may be supplied for MRD assessment. For participants who achieve a CR, bone marrow aspirates will be used for assessment of MRD by NGS of Ig heavy and light chains. If this methodology is unavailable, or determined to be scientifically inferior, then alternative methods for MRD assessment may be used.

8.2.1.7. Assessment of Lytic Disease

A complete skeletal survey (including skull, entire vertebral column, pelvis, chest, humeri, femora, and any other bones for which the investigator suspects involvement by disease) is to be performed and evaluated by the local laboratory by roentgenography (or the local standard of care imaging, eg, low-dose whole body CT) during the screening period. Please note that the same methodology used at screening should be used throughout the study for comparison purposes. During the treatment period and before disease progression is confirmed, imaging should be performed whenever clinically indicated based on symptoms or to document response or progression. Magnetic resonance imaging is an acceptable method for evaluation of bone disease and may be included as an additional assessment at the discretion of the investigator (see the disease response criteria in [Table 19](#)).

Participants may show disease progression manifested by symptoms of pain due to bone changes. Therefore, disease progression may be documented, in these cases, by skeletal survey or other radiographs, depending on the symptoms that the participant experiences. If the diagnosis of disease progression is obvious by radiographic investigations, then no repeat confirmatory imaging is necessary. In instances where changes may be subtler, repeat imaging may be performed in 1 to 3 weeks according to investigator discretion.

8.2.1.8. Assessment of Extramedullary Plasmacytomas

Sites of known extramedullary plasmacytomas must be documented during the screening period. Clinical examination or MRI may be used to document extramedullary sites of disease. Computed tomography scan evaluations are an acceptable alternative if there is no contraindication to the use of IV contrast. Positron emission tomography scan alone (ie, without a CT) or ultrasound tests are not acceptable to document the size of extramedullary plasmacytomas.

Extramedullary plasmacytomas should be assessed for all participants with a history of plasmacytomas or if clinically indicated at screening, by clinical examination or radiologic imaging. For participants with a history of plasmacytomas assessed by physical examination, physical examination should be repeated on Cycle 1 Day 1 if not done within 14 days before administration of study treatment. Assessment of measurable sites of extramedullary disease will be performed and evaluated locally approximately every 4 weeks by physical examination or approximately every 12 weeks by imaging (if required) for participants with a history of

plasmacytomas or as clinically indicated during treatment for other participants, until development of confirmed CR or confirmed disease progression. For every participant, the methodology used for evaluation of each disease site should be consistent across all visits. Irradiated or excised lesions will be considered not measurable and will be monitored only for disease progression.

To qualify for PR, the sum of products of the perpendicular diameters of the existing extramedullary plasmacytomas must have decreased by at least 50%, and new plasmacytomas must not have developed (see the disease response criteria in [Table 19](#)). To qualify for disease progression, either the sum of products of the perpendicular diameters of the existing extramedullary plasmacytomas must have increased by at least 50% or a new plasmacytoma must have developed. In the cases where not all existing extramedullary plasmacytomas are reported, but the sum of products of the perpendicular diameters of the reported plasmacytomas have increased by at least 50%, this will also qualify as disease progression.

8.2.2. Health Economics

Not applicable.

8.3. Safety Assessments

See Section [6.7](#) for guidelines regarding the management of relevant laboratory or other safety assessment abnormalities.

NOTE: As of Protocol Amendment 3, safety assessments are only required to be performed as per the site standard of care guidelines for the participant's condition and monitoring. Only SAEs, AESIs, and pregnancy will be collected in the eCRF.

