Urine sample for orotic acid	X	X*	X*		X				See Table 23 for sample collection times. * Cycle 1 only. Additional samples may be collected as clinically indicated. See Section 8.3.7.3 .			

Table 7: Schedule of Activities for All Participants (as of Protocol Amendment 3)

Procedure	Protocol Section	Treatment	EOT	Safety Follow-Up	Notes
		(28-Day Cycle)	+ 7 d	28-35 d After EOT	
Informed consent	8.1.1	X			Participants will sign a new ICF as per Protocol Amendment 3.
Contact IRT	8.1.3	X	X		
Concomitant medications	6.8	X	X	X	Review to ensure no prohibited medications are being used. Provide data to sponsor about medications used for SAEs and AESIs only.
Distribute reminder cards	8.1.4	X*	X		*On the clinic days for the next visit.
Assess study treatment compliance	6.4	X*	X		*Day 1 of each cycle.
Dispense/administer INCB001158 (participants receiving INCB001158 monotherapy or in combination with daratumumab SC)	6.1	X			On clinic day, INCB001158 should be given just before administration of daratumumab SC (if applicable). See Appendix B and Pharmacy Manual.
Administer daratumumab SC at site (participants receiving daratumumab SC monotherapy or in combination with INCB001158)	6.1	X			In clinic, daratumumab SC should be administered after INCB001158. See Appendix C and Pharmacy Manual.
AE assessments	8.3.1	X	X	X	All SAEs and AESIs must be recorded in the eCRFs, regardless of the causal relationship.
Efficacy/disease assessments (blood/urine/other)	8.2.1	X	X		As of Protocol Amendment 3, the disease assessments are only required to be performed as per standard of care guidelines for the participant's condition and monitoring.
Pregnancy testing	8.3.7.5	X*	X		All female participants of childbearing potential. *Urine at Day 1 of each cycle, at EOT, and as medically indicated or per country or institutional requirements.
Post-treatment anticancer therapy status	8.8.2			X	If a participant is scheduled to begin a post-treatment anticancer therapy before the end of the safety follow-up period, then the safety follow-up visit should be performed before post-treatment anticancer therapy is started.

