NOTE: As of Protocol Amendment 3, laboratory assessments should be performed in accordance with the standard of care of the investigational site for the participant's condition. Laboratory results do not need to be reported in the eCRF, but all laboratory results corresponding with an SAE or an AESI will be reported on the SAE form. In addition, pregnancy testing will continue to be performed for all participants as per the SoA in [Table 7](#).

Table 22: Required Laboratory Analytes

Chemistries	Hematology	Urinalysis With Microscopic Examination	Serology ^a
Albumin	Complete blood count, including:	Color and appearance	Hepatitis B surface antigen
Alkaline phosphatase	
 • Hemoglobin • Hematocrit • Platelet count • Red blood cell count • White blood cell count 	pH and specific gravity	Hepatitis B surface antigen antibody
ALT		Bilirubin	Hepatitis B core antibody
Ammonia		Glucose	HBV DNA
Amylase		Ketones	HCV antibody
██████████		Leukocytes	HCV RNA
AST		Nitrite	HIV RNA (if required by local regulations)
Bicarbonate or CO ₂	Differential count, including:	Occult blood	
BUN or urea	
 • Basophils • Eosinophils • Lymphocytes • Monocytes • Neutrophils 	Orotic acid ^b	
Calcium		Protein	
Chloride			
Creatinine			
Glucose			
Lactate dehydrogenase	Absolute values must be provided for:		
Lipase	
 • WBC differential laboratory results 		
██████████	
 • Blood type test^c 		
Phosphate			
Potassium			
Sodium			
Total bilirubin			
Direct bilirubin (if total bilirubin is elevated above ULN)			
Total protein			
Uric acid			
Lipid Panel		Pregnancy Testing	
		Total cholesterol	Female participants of childbearing potential require a serum pregnancy test at screening and a urine pregnancy test on Day 1 of every cycle, at EOT, and as medically indicated or per country or institutional requirements.
		Triglycerides	
		LDL	
		HDL	
Thyroid panel		Pregnancy tests (serum or urine) should be repeated if required by local regulations.	
		TSH	
		FT4	
		FT3/T3	

Note: Additional tests may be required, as agreed upon by the investigator and sponsor, based on emerging safety data.

^a Hepatitis B and C viral loads by PCR assay only need to be assessed when respective serology results are positive. Hepatitis B virus DNA does not need to be performed if the surface antibody is the only positive result.

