8.8.3. Survival Follow-Up

Once a participant has received the last dose of study drug, has confirmed disease progression, or starts a new anticancer therapy, the participant moves into the survival follow-up period and should be contacted by telephone, email, or visit at least every 12 weeks following EOT to assess for survival status until death, withdrawal of consent, or the end of the study, whichever occurs first.

For participants having entered the survival follow-up period of the study, the site will use continuing participant records to supply data on subsequent treatment regimens, disease assessments (if discontinued treatment for a reason other than progression), and OS in the eCRF. For participants who do not intend to return to the study investigator for their ongoing care, follow-up should be maintained by phone contact, patient records, and public records/databases at intervals of no longer than 12 weeks.

NOTE: As of Protocol Amendment 3, the survival follow-up visits for participants who discontinue study treatment for a reason other than disease progression are no longer required beyond the safety follow-up visit. The last survival follow-up data will be recorded in the eCRF at the time of the safety follow-up visit. The last study visit will be the safety follow-up visit.

9. ADVERSE EVENTS: DEFINITIONS AND PROCEDURES FOR RECORDING, EVALUATING, FOLLOW-UP, AND REPORTING

NOTE: As of Protocol Amendment 3, the only safety data that will be collected will be related to SAEs, AESIs, and pregnancy. The safety follow-up visits may be completed remotely (such as by televisit).

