APPENDIX F. PROTOCOL AMENDMENT SUMMARY OF CHANGES

Document	Date
Amendment (Version) 1-EU:	18 MAR 2019
Amendment (Version) 1-DE:	16 JUL 2019
Amendment (Version) 2:	12 OCT 2020
Amendment (Version) 3:	01 DEC 2021

Amendment 3 (01 DEC 2021)

Overall Rationale for the Amendment: The primary purpose of this amendment is to provide guidance for the management of ongoing participants, as enrollment has been terminated and sufficient data have been collected for safety analysis.

1. **Protocol Summary (Table 2: Key Study Design Elements; Table 7: Schedule of Activities for All Participants [as of Protocol Amendment 3]; Section 4.1, Overall Design; Section 4.2, Overall Study Duration; Section 6.3, Measures to Minimize Bias: Randomization and Blinding; Section 6.7.4, Dose Delays and Dose Modification of Daratumumab SC; Section 6.8, Concomitant Medications and Procedures; Section 7.1.2, Discontinuation Procedures; Section 7.2, Participant Withdrawal From the Study; Section 8.2, Efficacy Assessments; Section 8.2.1.1, Responses Categories; Section 8.2.1.2, Myeloma Protein Measurements in Serum and Urine; Section 8.2.1.3, Serum Calcium Corrected for Albumin; Section 8.3, Safety Assessments; Section 8.3.7, Laboratory Assessments; Section 8.8.1, Safety Follow-Up; Section 8.8.2, Disease Status Follow-Up; Section 8.8.3, Survival Follow-Up; Section 9, Adverse Events: Definitions and Procedures for Recording, Evaluating, Follow-Up, and Reporting; Section 9.4, Reporting of Serious Adverse Events; Section 9.5, Adverse Events of Special Interest; Section 9.7, Pregnancy; Appendix B, Instruction to Participants For Handling Study Drug (INCB001158)**

Description of change: Study assessments for all participants remaining on study treatment have been limited to standard of care for the participant's condition. Safety data will only be collected for SAEs and AESIs, and disease status and survival follow-up data will only be collected until the last safety follow-up visit.

Rationale for change: To update the study assessments for all ongoing participants.

2. **Protocol Summary (Table 2: Key Study Design Elements); Section 11.1.1, Identification of the Coordinating Principal Investigator**

Description of change: Included the process for identification of the coordinating principal investigator.

Rationale for change: To update applicable sections as per current protocol template.

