2. STUDY INFORMATION, OBJECTIVES, AND ENDPOINTS

2.1. Protocol and Case Report Form Version

This SAP is based on INCB 01158-206 Protocol Amendment 3 dated 01 DEC 2021 and CRFs approved 09 JUL 2021. Unless superseded by an amendment, this SAP will be effective for all subsequent Protocol amendments and eCRF versions.

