8.2. Adverse Events

8.2.1. Adverse Event Definitions

A TEAE is any AE either reported for the first time or worsening of a pre-existing event after the first dose of study drug. Analysis of AEs (as discussed below) will be limited to TEAEs, but data listings will include all AEs regardless of their timing in relation to study drug administration. For purposes of analysis, all AEs will be considered TEAEs unless the AE can unequivocally be defined as not treatment-emergent.

Adverse events will be tabulated by MedDRA PT and SOC. Severity of AEs will be graded using the NCI CTCAE v5. The CTCAE reporting guidelines and grading details are available on the Cancer Therapy Evaluation Program website.

The subset of AEs considered by the investigator to be related to study drug will be considered to be treatment-related AEs. If the investigator does not specify the relationship of the AE to study drug, the AE will be considered to be treatment-related. The incidence of AEs and treatment-related AEs will be tabulated. In addition, serious TEAEs will also be tabulated.

A grading (severity) scale is provided for each AE term. If the toxicity is not included in the CTCAE v5 criteria, it will be rated on a scale of 1 to 5 as follows: 1 = mild, 2 = moderate, 3 = severe, 4 = life threatening, and 5 = death related to AE. All toxicities will be graded based on the worst level reached, not the level they may have reached if they had not been treated. When the intensity of an AE changes over time for a reporting period (eg, between visits), each change in intensity will be collected as an AE until the event resolves. Only the worst grade will be reported in AE summaries. Also, Grade 3 or higher AEs will be summarized.

Any missing onset date, causality, or severity must be queried for resolution. Unresolved missing causality and severity will be handled according to the following rules:

- An unresolved missing causality will be considered treatment-related.
- An unresolved missing severity will be identified as an unknown severity.

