8.2.4. Adverse Event Summaries

An overall summary of AEs by dose level for Phase 1 and by treatment group for Phase 2 using the FAS population as applicable will include the following:

- Number (%) of participants reporting any TEAEs
- Number (%) of participants reporting any serious TEAEs
- Number (%) of participants reporting any Grade 3 or higher TEAEs
- Number (%) of participants who had a fatal TEAE
- Number (%) of participants who had a TEAE related to INCB001158
- Number (%) of participants who had a TEAE related to daratumumab SC
- Number (%) of participants who had a TEAE related to INCB001158 and/or daratumumab SC
- Number (%) of participants who had a Grade 3 or higher TEAE related to INCB001158
- Number (%) of participants who had a Grade 3 or higher TEAE related to daratumumab SC
- Number (%) of participants who had a Grade 3 or higher TEAE related to INCB001158 and/or daratumumab SC
- Number (%) of participants who had a serious TEAE related to INCB001158
- Number (%) of participants who had a serious TEAE related to daratumumab SC
- Number (%) of participants who had a serious TEAE related to INCB001158 and/or daratumumab SC

- Number (%) of participants who had a TEAE leading to temporary interruption of INCB001158
- Number (%) of participants who had a TEAE leading to INCB001158 dose reduction
- Number (%) of participants who had a TEAE leading to permanent discontinuation of INCB001158
- Number (%) of participants who had an irAE

The following summaries will be produced by MedDRA term for the Phase 1 and Phase 2 FAS population (if 10 or fewer participants appear in a table, a listing may be appropriate):

- Summary of TEAEs by SOC and PT
- Summary of TEAEs by PT in decreasing order of frequency
- Summary of Grade 3 or higher TEAEs by PT in decreasing order of frequency
- Summary of serious TEAEs by PT in decreasing order of frequency
- Summary of INCB001158 treatment-related TEAEs by PT in decreasing order of frequency
- Summary of Grade 3 or higher INCB001158 treatment-related TEAEs by PT in decreasing order of frequency
- Summary of TEAEs with a fatal outcome by SOC and PT
- Summary of TEAEs leading to INCB001158 dose reduction by PT in decreasing order of frequency
- Summary of TEAEs leading to INCB001158 dose interruption by PT in decreasing order of frequency
- Summary of TEAEs leading to discontinuation of INCB001158 by PT in decreasing order of frequency

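### From Amendment 3 only SAEs, AESIs and pregnancy are collected, but the SAP's all-TEAE tables have no end of window and sit beside exposure counted to last dose

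*Protocol*

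**What the plan says.** **What is collected.** Protocol Section 8.3 moves safety assessments to site standard of care from Amendment 3 and adds: "Only SAEs, AESIs, and pregnancy will be collected in the eCRF". The opening note of Section 9 repeats it: "the only safety data that will be collected will be related to SAEs, AESIs, and pregnancy". Section 8.3.7 says of laboratory data: "Laboratory results do not need to be reported in the eCRF"; results tied to an SAE or AESI go on the SAE form. Section 6.8 limits concomitant-medication entry to what relates to SAEs or AESIs. Table 7, the only schedule in force from Amendment 3, has no rows for vital signs, ECG or routine safety laboratory tests apart from pregnancy testing. It keeps dispensing, administration and compliance checks.

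**Who is affected.** Appendix F gives the purpose of Amendment 3 as "guidance for the management of ongoing participants, as enrollment has been terminated and sufficient data have been collected for safety analysis". Table 7 adds: "Participants will sign a new ICF as per Protocol Amendment 3".

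**What is analysed.** SAP Section 2.1 states: "This SAP is based on INCB 01158-206 Protocol Amendment 3 dated 01 DEC 2021 and CRFs approved 09 JUL 2021". SAP Section 8.2.1 counts as treatment-emergent any event that is new or worse after first dose, sets no end to the window, and says: "Analysis of AEs (as discussed below) will be limited to TEAEs". Section 8.2.4 then plans, among others, "Summary of TEAEs by SOC and PT", together with tables of Grade 3 or higher events, INCB001158-related events, and events leading to dose reduction, interruption or discontinuation. Section 8.3.2 summarizes laboratory worsening by maximum severity without a cut-off. Section 6.4.1 counts INCB001158 treatment duration from first to last dose. Section 10.1 records only the dropped efficacy analyses as a change from the protocol.

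**The concern.** Efficacy is reduced to listings, so the safety tables are the only formal results. The Phase 1 primary endpoint, which is also a Phase 2 secondary endpoint, is the frequency, duration and severity of AEs.

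After the switch, a continuing participant who has a first non-serious, non-AESI event has nowhere to record it. In an all-TEAE table that participant looks the same as one who was fully observed and had no event. The exposure table beside it credits the whole time to last dose. A reader who sets one against the other treats uncollected time as event-free. The same table still gains SAEs and AESIs from the later period, so its mix of event types depends on when each participant's collection changed. Results are shown by dose level and treatment group, so the shortfall differs between columns wherever treatment time after the switch differs.

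**Working it through.** The plan gives no figure to reproduce: no sample size, power or error rate bears on this point. The check sets the texts side by side, then does the date arithmetic and a labelled illustration.

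**1. Collection against analysis, after the switch**

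| Data | Collected after Amendment 3? | SAP treatment | Consequence |
|---|---|---|---|
| Non-serious, non-AESI AEs | No | In all-TEAE, Grade 3 or higher, related and dose-modification tables, no end date | Incidence understated over the reported treatment period |
| SAEs, including fatal AEs; AESIs, including irAEs | Yes | Same tables, plus serious, fatal and irAE summaries | Serious, fatal and irAE results largely unaffected |
| Routine laboratory, vital signs, ECG | Not required in the eCRF, or not scheduled | By-visit summaries; laboratory worsening by maximum severity; abnormal vital signs and ECG outliers | By-visit tables mainly lose observations; worst-grade and outlier counts are under-ascertained |
| Concomitant medications | Only with SAEs or AESIs | Counted for the FAS | Understated after the switch |
| Study treatment | Dosing continues | Duration counted to last dose | Correct as exposure, longer than full AE collection |
| DLTs | Fixed 28-day window | Listed | Affected only if someone was in Cycle 1 at the switch, very unlikely with enrollment ended |

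The only cut-off in the SAP is an undated clinical data cut-off used to censor overall survival (Section 7.3.2.5). It is not applied to any safety table.

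**2. How long the gap could be.** Amendment 3 is dated 01 DEC 2021 and the SAP 19 APR 2022. The interval is 30 + 31 + 28 + 31 + 19 = 139 days, and 139/28 = 4.96 cycles. A participant still on treatment could have about five cycles of counted exposure without full AE collection before the SAP was written. The switch follows re-consent, so its date differs by participant.

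**3. Illustration (all values assumed).** Everyone has 6 cycles of full collection. A share s of the group then has 5 further treated cycles after the switch. The hazard of a first non-serious, non-AESI event of one type is h per cycle.

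- Shown in the table: 1 − exp(−6h)
- With full collection throughout: (1 − s)[1 − exp(−6h)] + s[1 − exp(−11h)]
- Gap: s[exp(−6h) − exp(−11h)]

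| h | Shown | Complete, s = 10% | s = 30% | s = 50% | Gap (points) |
|---|---|---|---|---|---|
| 0.02 | 11.3% | 12.2% | 13.8% | 15.5% | 0.8 to 4.2 |
| 0.05 | 25.9% | 27.6% | 30.8% | 34.1% | 1.6 to 8.2 |
| 0.10 | 45.1% | 47.3% | 51.6% | 55.9% | 2.2 to 10.8 |

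At s = 0 the gap is zero. The documents give neither s nor the treatment time after the switch, so they cannot place the trial in this range.

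**The case against.** The strongest reply is that cutting the tables at the switch changes almost none of the affected percentages. The SAP reports numbers and percentages of the FAS, with no exposure-adjusted rates. Non-serious events after the switch are not in the data, so truncation leaves numerator and denominator as they were. It mainly removes later SAEs and AESIs from the all-TEAE tables. This is correct. The gain is that the window is stated and paired with matching exposure, so the percentage describes a period in which such events could be recorded. Nothing restores the missing events.

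Four stronger readings are tempting but unsupported:

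- *Reported exposure is wrong.* SAP Section 6.4.1 defines duration of treatment, not observation time. Drug taken after the switch is real exposure and should stay in the report.
- *The groups treated longest are worst affected.* The shortfall follows treatment time after the switch. A participant treated for a long time who stopped before it is fully ascertained, and the documents do not show which dose levels or groups overlapped it.
- *About 27% to 32% of events are missed.* That follows from an assumed participant with 12 months on treatment, the last 4 under Amendment 3, and a constant monthly risk of 5% or 1% (33.7% observed against 46.0%, or 7.7% against 11.4%). As a table-level figure it would require every participant to have that profile.
- *All the main safety results are biased.* SAEs and AESIs are still collected, and AESIs cover the immune-related and urea-cycle risks, including laboratory abnormalities.

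Appendix F also says enough data had been collected for safety analysis, and Protocol Section 4.2 permits a database lock with 5 or fewer participants remaining. Both suggest the effect may be small. Neither sets a cut-off for a safety table, and the first is itself a reason to end the full-collection tables at the switch.

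**Conclusion.** The point holds as a mismatch of windows. The SAP is written on an amendment that stops collecting non-serious, non-AESI events and most routine safety data, but it neither ends the affected tables there nor discloses the change. For any participant treated after the switch, the all-TEAE, non-serious Grade 3 or higher, treatment-related and dose-modification tables understate incidence over the reported treatment period and combine two levels of ascertainment. Worst-grade laboratory results share the problem.

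The size is unknown. The 0.8 to 10.8 points rest on a constant hazard, 6 cycles before and 5 after the switch, and 10% to 50% of participants continuing. The true value is zero if nobody was treated after the switch, and the documents say only that participants were ongoing when the amendment was written. The correction is worth making because safety is the only formal analysis left and the cost is small.

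**What to change.** Amend SAP Sections 6.4, 6.6, 8.2 to 8.5 and 10.1, and Appendix A:

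- Define for each participant a full-collection end date, the date of the switch to Amendment 3. Re-consent is the natural marker.
- Present the all-TEAE tables (with their Grade 3 or higher, related and dose-modification subsets) and the worst-grade laboratory, vital-sign, ECG and concomitant-medication tables up to that date, and label them so.
- Report exposure within that window in addition to, not instead of, total exposure to last dose.
- Present serious TEAEs, fatal TEAEs and AESIs over the full period. Add to Appendix A the serious-TEAE table by preferred term that Section 8.2.4 specifies; Tables 3.2.1 to 3.2.10 do not include it, although the overall summary and Listing 2.7.3 cover serious events in part.
- State by dose level or treatment group how many participants continued after the switch and for how long.
- Record the reduced collection and its handling in Section 10.1.

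The cost is SAP wording, one date flag per participant and one added table, with no new clinical data. A few serious or AESI events after the switch move out of the all-TEAE tables into the full-period ones. If nobody was treated after the switch, one sentence saying so is enough.
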